1. LIST OF ABBREVIATIONS

Abbreviation	Definition
CCI	
AE	Adverse Event
AEM	Adverse Event Monitoring
ALL	Acute Lymphoblastic Leukemia
ANC	Absolute Neutrophil Count
ADL	Activities of Daily Living
BSA	Body Surface Area
CI	Confidence Interval
CR	Complete response /Complete remission
CRF	Case Report Form
CRi	Complete response with incomplete blood count recovery /Complete remission with incomplete hematologic recovery
CTCAE	Common Terminology Criteria for Adverse Events
HCT	Hematopoietic Cell Transplant
IEC	Independent Ethics Committee
IgG4	Immunoglobulin type G, subtype 4
IRB	Institutional Review Board
MFDS	Ministry of Food and Drug Safety
NCI	National Cancer Institute
NI	Non-Interventional
NIS	Non-Interventional Study
PMS	Post-Marketing Surveillance

RMP	Risk Management Plan
SAE	Serious Adverse Event
SAP	Statistical Analysis Plan
SRSD	Single Reference Safety Document
VOD/SOS	Veno-Occlusive liver Disease/ Sinusoidal Obstruction Syndrome

3. AMENDMENTS AND UPDATES

Amendment number	Date	Protocol section(s) changed	Summary of amendment(s)	Reason
Amendment 1	13Nov 2018	2.Responsible parties	Change of Principal Investigator(s) of the Protocol	Resignation of responsible colleague
		7.3.8.3. Adverse events data collection	Change of category for action/outcome	Align with AEM01 - Form guidance - NIS WIITH Stipulated Collection of AEs/Pragmatic Non-Medicinal Interv Study Completion Guide (V6:Aug-2016)
		7.4. Sample size	Description the Section of Regulation on Approval and Review of Biological Products and re-state the reference for sample size	Describe relevant law in detail and state more proper reference for sample size
		7.5.Data source	Delete duplicated section and move some section to 7.6.1	
		7.5.2 Record retention	Move to 7. 6. 2	
		7.6.1 CRFs/DCTs /Electronic data record	Add data management section	Align with CT24-WI-GL02-RF01 1.0 Non-Interventional Study Protocol Template For Primary Data Collection Study 15-Aug-2018
		8. Protection of human subjects	Re-state in detail	
Amendment 2	27Mar2019	4. Milestones	Change of Planned date for milestones	Change of Planned date according to the actual date of BESPONSA® approval.
		7.2.3. Duration of the study	Add definition in the duration of the study	Due to MFDS corrective order
Amendment 3	19 Jun 2023	2.Responsible parties	Change of Principal Investigator(s) of the Protocol	Resignation of responsible colleague
		5. Rationale and background	Change of the number of subjects Update result of Phase 3 INOVATE study	Changes based on the adjustment application for the number of subjects To reflect final result
		7.2.3. Duration of the study	Change of the number of subjects	Changes based on the adjustment application for the number of subjects
		7.4. Study Size	Change of the number of subjects	Changes based on the adjustment application for the number of subjects
Amendment 4	07 Nov 2023	5. Rationale and background	Change of the number of subjects	Changes based on the adjustment application for the number of subjects
		7.2.3. Duration of the study	Change of the number of subjects	Changes based on the adjustment application for the number of subjects
		7.3.8.2. Definition of serious adverse events (SAEs)	Revision of description for Hospitalization	Reflection of the updated Pfizer SOP template
		7.4. Study Size	Change of the number of subjects	Changes based on the adjustment application for the number of subjects
		7.6.2. Record	Changes of record retention	Reflection of the updated Pfizer SOP

BESONSA® (Inotuzumab Ozogamycin)
<B1931027> NON-INTERVENTIONAL STUDY PROTOCOL
Amendment 4, 07 Nov 2023

	retention	period	template
	9.4.3. Scenarios necessitating reporting to Pfizer Safety within 24 hours	Revision of description for Exposure during pregnancy	Reflection of the updated Pfizer SOP template

[figure not shown]
4. MILESTONES

Milestone	Planned date
BESPONSA® approval	3 Jan 2019
Start of data collection	1 Jun 2019
End of data collection	2 Jan 2025
Interim report As required by MFDS regulations, the periodic interim report along with RMP report would be submitted to MFDS every 6 months for the first two years and then annual report would be submitted to MFDS for the third, fourth and fifth year. The final report would be submitted in the sixth year refer to RMP milestone.	2 Sep 2019 2 Mar 2020 2 Sep 2020 2 Mar 2021 2 Mar 2022 2 Mar 2023 2 Mar 2024
MFDS re-examination report	2 Apr 2025

5. RATIONALE AND BACKGROUND

Acute lymphoblastic leukemia (ALL) is a rare, serious, and life-threatening condition with a need for improved therapies. Relapsed or refractory B-cell ALL is a fatal disease with a median survival time in adults of only approximately 3-6 months^{1 2}. The age adjusted incidence rate of ALL in the United States is 1.7 per 100,000 individuals per year³, with approximately 6,020 new cases and 1,440 deaths estimated in 2014⁴. While the cure rates and survival outcomes for B-cell ALL have improved during the last several decades, most of the improvements have occurred in younger patients, primarily among children. Recent improvements are largely due to advances in the understanding of the molecular genetics and pathogenesis of B-cell ALL, incorporation of risk-adapted therapy and the advent of targeted agents.

CCI

Before the approval of BESPONSA® in Korea, this non-interventional study is designated as a Post-Marketing Surveillance (PMS) Study and is a commitment to Ministry of Food and Drug Safety (MFDS), as a part of Risk Management Plan (RMP) which is required by MFDS.

PFIZER CONFIDENTIAL

CT24-WI-GL02-RF01 6.0 Non-Interventional Study Protocol Template For Primary Data Collection Study 01-

Aug-2023

Page 10 of 37

The safety and effectiveness information of BESPONSA® will be gathered at minimum 100 subjects administered in the setting of routine practice in Korea during the initial 6 years after the approval.

6. RESEARCH QUESTION AND OBJECTIVES

The objectives of this study are to determine any problems or questions associated with BESPONSA® after marketing, with regard to the following clauses under conditions of general clinical practice, in compliance with the regulation “Re-examination Guideline of New Drugs, Etc” (Ministry of Food and Drug Safety Notification 2015-79, 2015.10.30, amended).

- (1) Serious adverse event/adverse drug reaction
- (2) Unexpected adverse event/adverse drug reaction that has not been reflected in the approved drug label.
- (3) Known adverse drug reaction
- (4) Non-serious adverse drug reaction
- (5) Other safety and effectiveness information

7. RESEARCH METHODS

7.1. Study design

This is a prospective, observational, non-interventional, multi-center study in which subjects will be administered as part of routine practice at Korean health care centers by accredited physicians. The study can be performed in Korean health care centers where BESPONSA® is prescribed to treat the relapsed or refractory B-cell precursor ALL.

7.2. Setting

All subjects enrolled should meet the usual prescribing criteria for BESPONSA® as per the local product document (LPD) and should be entered into the study at the physician's discretion.

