7.2.3. Duration of the study

According to MFDS re-examination regulation, the re-examination report based on collected data of 6 years must be submitted to MFDS within 3 months after the end of specified re-examination period (from the product approval date to 6 years afterwards).

The data collection period of this study is until the required subject number (100 patients) is collected. The observation period for each subject is from initiating administration of first dose of BESPONSA® to the end of the observation period of the study, which must include at least 28 calendar days following the last administration of a BESPONSA®. In case of patient that Hematopoietic Stem Cell Transplant (HSCT) after administrated BESPONSA®, follow-up until 180 days after transplantation. All the data collected during the observation period should be recorded in the case report form (CRF). In case of an adverse event/safety event recognized after the observation period ends, it should be recorded in the CRF as specified in Section 7.

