his or her own consent, the source documents must record why the patient did not provide consent (e.g., minor, decisionally impaired adult), how the investigator determined that the person signing the consent was the patient's legally acceptable representative, the consent signer's relationship to the study patient (e.g., parent, spouse), and that the patient's assent was obtained or waived. If assent is obtained verbally, it must be documented in the source documents.

The investigator, or a person designated by the investigator, will obtain written informed consent from each patient or the patient's legally acceptable representative, parent(s), or legal guardian and the patient's assent, when applicable, before any study-specific activity is performed unless a waiver of informed consent has been granted by an IRB/IEC. The investigator will retain the original of each patient's signed consent document.

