9.2. Reporting period

For each patient, the safety event reporting period begins at the time of the patient's first dose of BESPONSA®, or the time of the patient's data privacy statement if s/he is already exposed to BESPONSA®, and lasts through the end of the observation period of the study, which must include at least 28 calendar days following the last administration of a drug under study; a report must be submitted to Pfizer Safety (or its designated representative) for any of the types of safety events listed in the table above occurring during this period. If a patient was administered a drug under study on the last day of the observation period, then the reporting period should be extended for 28 calendar days following the end of observation.

Most often, the date of data privacy statement is the same as the date of enrollment. In some situations, there may be a lag between the dates of data privacy statement and enrollment. In these instances, if a patient provides data privacy statement but is never enrolled in the study (e.g., patient changes his/her mind about participation), the reporting period ends on the date of the decision to not enroll the patient.

If the investigator becomes aware of a SAE occurring at any time after completion of the study and s/he considers the SAE to be related to BESPONSA®, the SAE also must be reported to Pfizer Safety.

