4. HYPOTHESES AND DECISION RULES

There is no formal research hypothesis for this study. The purpose of the study is to assess real-life safety and effectiveness of BESPONSA® in Korean adult patients with relapsed or refractory B-cell precursor acute lymphoblastic leukemia (ALL) using the descriptive statistics. For the exploratory analysis, statistical tests may be performed. P-values may be provided, but no definite conclusions will be made based on p-values and no adjustments for multiplicity will be applied.

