5.1 SAFETY ANALYSIS SET

The safety analysis set includes patients who have been administered BESONSA® at least once and evaluated with safety-related endpoints at least once.

Patients meeting any of the following criteria will be excluded in the safety analysis set.

1. Patients who received BESONSA® prior to site initiating contract date
2. Patients who didn't receive BESONSA®
3. Safety follow-up failure: Patients without documented evidence for whom adverse event status was evaluated(Patients with "Whether AE status was evaluated" checked as No in the eCRF OR no answer is provided to question "Whether a patient has AE" in the eCRF)
4. Patients who violated inclusion/exclusion criteria
5. Patients who violated usage
6. Patients who have enrolled twice or more (i.e. if a patient has been assigned to two or more subject ID or CRFs, only one record clarified by site will be used for analysis and the others will be excluded)

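### Entry is at the physician's discretion and can follow the first dose, so inclusion can depend on early outcome and the results may differ from those of all treated patients by an unknown amount

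*Protocol*

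**What the plan says.** - **Who enters.** Protocol 7.2 requires subjects to meet the usual prescribing criteria and adds that they "should be entered into the study at the physician's discretion". SAP 2.1 repeats this. The discretion concerns study entry; prescribing is dealt with separately in the same sentence. Protocol 7.3.1 numbers patients sequentially, but this numbers only those who were chosen.
- **When they enter.** Protocol 7.1 reads "This is a prospective, observational, non-interventional, multi-center study". Protocol 9.2 starts safety reporting at the first dose, "or the time of the patient's data privacy statement if s/he is already exposed to BESPONSA". Protocol 8.2 requires consent "before any study-specific activity is performed unless a waiver of informed consent has been granted by an IRB/IEC", which is not the same as before the first dose when the data come mostly from patient charts (7.5).
- **When observation starts.** Protocol 7.2.3: "The observation period for each subject is from initiating administration of first dose of BESPONSA", with no exception for later entrants.
- **The safeguard.** SAP 5.1 removes from the safety set, and so through 5.2 from the effectiveness set, "Patients who received BESONSA® prior to site initiating contract date".
- **The aim.** Protocol 6 looks for problems "under conditions of general clinical practice". SAP 4 adds: "The purpose of the study is to assess real-life safety and effectiveness of BESPONSA® in Korean adult patients".
- **Limitations.** Protocol 7.9 refers in general terms to an uncontrolled, non-randomised observational design. It does not mention selective or late entry.

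**The concern.** The aim is to describe what happens to patients treated in ordinary practice. That needs the entered patients to resemble the treated patients, or at least a record of how they differ. Here the physician chooses whom to enter. If the patient was dosed after the contract date, the choice can be made once early toxicity or the first response is known. A patient who deteriorates in the first cycle may never be approached.

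The numerator and denominator of every response and adverse event percentage then rest on a selection that may be linked to outcome. The Clopper-Pearson intervals in SAP 8.1.3 cover random error only. PFS and OS are affected too: the SAP measures both from enrollment, so a late entrant is included only after surviving from first dose to entry, and that interval is not counted.

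**Working it through.** The documents contest no figure here. The target of 100 patients has no visible precision or power basis (the justification is redacted), so there is nothing to reproduce. The check has two parts.

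**1. What the plan can and cannot detect**

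| Type of selection | Information available | Detectable? |
|---|---|---|
| Entry after first dose | Date of signing the privacy statement (Protocol 7.3.1) and administration dates (7.3.6), both on the CRF | Yes, per patient, but no analysis is planned |
| Treated but never entered | No log or site count in either document | No |

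The SAP's contract-date exclusion narrows the first type but does not close it. A patient first dosed after the contract date and entered some weeks later stays in both analysis sets.

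**2. How large the effect could be**

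All rates below are assumptions; the visible documents give none of them. The 100 patients and the exact 95% interval come from the plan.

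*Response.* Let p be the true response rate and r the probability that a responder is entered divided by that for a non-responder. The expected observed rate is p·r / (p·r + 1 − p). Coverage is the probability that the exact 95% interval from 100 patients contains p.

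| True p | r | Expected observed rate | Coverage of p |
|---|---|---|---|
| 50% | 0.67 | 0.335/0.835 = 40.1% | 55% |
| 50% | 1 | 50.0% | 96.5% |
| 50% | 1.25 | 0.625/1.125 = 55.6% | 84% |
| 50% | 1.5 | 0.75/1.25 = 60.0% | 54% |
| 50% | 2 | 1.00/1.50 = 66.7% | 10% |
| 70% | 0.67 | 0.469/0.769 = 61.0% | 54% |
| 70% | 1.5 | 1.05/1.35 = 77.8% | 65% |
| 70% | 2 | 1.40/1.70 = 82.4% | 22% |

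For comparison, 50 responders in 100 give an exact interval of 39.8% to 60.2%, a half-width of about 10 points. At p = 50%, a 1.5-fold preference produces a bias of the same size. A larger sample would narrow the interval and leave the bias.

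*Early deaths.* Let q be the true share dying in an early window, and s the share of patients who would be entered only after that window. The observed share is q(1 − s) / (q(1 − s) + 1 − q). With q = 10%:

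- s = 25%: 0.075/0.975 = 7.7%
- s = 50%: 0.05/0.95 = 5.3%

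With q = 5% the results are 3.8% and 2.6%; with q = 15% they are 11.7% and 8.1%.

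**Start of safety data for late entrants.** Protocol 7.2.3 starts observation at first dose for every subject, and 7.3.8.3 collects adverse events over that period. Protocol 9.2 starts safety reporting at signature for patients already exposed. One could read these together (CRF back to first dose, reports to the sponsor's safety unit from signature), but the documents do not say so, and sites could record events before signature inconsistently.

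**The case against.** Four points against a stronger reading stand.

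- **A reader might infer that the rates do not describe routine practice, or are too favourable.** The documents show only that they may differ. In a safety surveillance a physician could equally favour patients who have had events, and the table shows the result for r below 1.
- **A reader might take the 3 to 6 month median survival in Protocol 5 to mean that the missed group is large.** That figure is background on relapsed or refractory adult disease. It is not stated for patients on this drug and says nothing about deterioration in the first cycle.
- **A reader might conclude that no analysis can help.** That holds for patients never entered, not for late entry, which the CRF dates reveal. SAP 8.2.5 also tabulates spontaneously reported events, so a reaction outside the study can still be seen. Without a denominator, though, this does not repair any percentage.
- **Late entry may be rare.** Protocol 9.2 is a reporting clause, not an eligibility rule, and nothing shows how often it applies.

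It can also be said that discretion is normal in a non-interventional study, that the regulator shapes the design (Protocol 7.9), and that the analysis is descriptive with no hypothesis (SAP 4). Non-intervention protects the treatment decision, however, and inviting every treated patient leaves that untouched. A descriptive percentage still needs a defined population.

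Timing is the strongest practical objection. Collection was planned from 1 June 2019 to 2 January 2025 and Amendment 4 is dated 7 November 2023, so even a rule in that version would have covered only about the last 14 of 67 months.

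**Conclusion.** The concern holds in limited form. Entry is discretionary, it can follow exposure, and the contract-date exclusion is the only restraint. Inclusion can therefore depend on early response or toxicity, and the response, adverse event, PFS and OS results may differ from those of all treated patients. A favourable bias is plausible but not certain, and its size is unknown. Under the assumed preferences of 1.25 to 2-fold, at a true response of 50%, the shift is about 6 to 17 points; a preference of 0.67 shifts it about 10 points the other way. These figures show only that moderate selection can match or exceed the random error at 100 patients. They do not estimate what happened. Late entry can be measured from data already collected; selection among patients never entered cannot be detected under the plan. The point deserves correction, mainly because part of the remedy is cheap.

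**What to change.** 1. **SAP, using existing data.** Compare the privacy-statement date with the first administration date. Report the number entered after first dose and the interval between the two dates. Show response and adverse event rates, PFS and OS also for patients entered on or before first dose. This costs one table split. The subgroup is smaller, so its intervals are wider, and it is still a discretionary sample: the split removes selection on outcomes after dosing, not selection on prognosis before it.
2. **Protocol 7.2 and SAP 2.1, for remaining accrual.** Replace the discretion clause with an invitation to all consecutive patients starting the drug at contracted sites, at or before first dose where possible. State that the prescribing decision remains the physician's. Report in Table 1 a per-site count of treated patients not entered. Treatment and sample size do not change.
3. **Protocol 7.9.** Name selective and late entry as limitations, with the direction given as uncertain.
4. **Protocol 7.2.3 and 9.2.** Reconcile when observation and safety reporting start for patients already exposed.

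The cost of items 2 to 4 is some site work, a protocol amendment with IRB/IEC approval where applicable (Protocol 8.4), and, for item 2, a recruitment rule that changes part-way through the study, so the report should give the date of the change. If accrual is effectively complete, items 1 and 3 still apply.

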7.2.1. Inclusion criteria

Patients must meet all of the following inclusion criteria to be eligible for inclusion in the study:

PFIZER CONFIDENTIAL

CT24-WI-GL02-RF01 6.0 Non-Interventional Study Protocol Template For Primary Data Collection Study 01-

Aug-2023

Page 11 of 37

1. Patients diagnosed as relapsed or refractory B-cell precursor lymphoblastic leukemia (ALL).
2. Evidence of a personally signed and dated informed consent document indicating that the patient (or a legally acceptable representative) has been informed of all pertinent aspects of the study.

7.2.2. Exclusion criteria

Patients meeting any of the following criteria will not be included in the study:

1. Any patients who does not agree that Pfizer and companies working with Pfizer use his/her information.
2. Patients to whom BESPONSA® is contraindicated as per the local labeling.

7.2.3. Duration of the study

According to MFDS re-examination regulation, the re-examination report based on collected data of 6 years must be submitted to MFDS within 3 months after the end of specified re-examination period (from the product approval date to 6 years afterwards).

The data collection period of this study is until the required subject number (100 patients) is collected. The observation period for each subject is from initiating administration of first dose of BESPONSA® to the end of the observation period of the study, which must include at least 28 calendar days following the last administration of a BESPONSA®. In case of patient that Hematopoietic Stem Cell Transplant (HSCT) after administrated BESPONSA®, follow-up until 180 days after transplantation. All the data collected during the observation period should be recorded in the case report form (CRF). In case of an adverse event/safety event recognized after the observation period ends, it should be recorded in the CRF as specified in Section 7.

7.2.4. Dosage and administration

The use and dosage recommendations for BESPONSA® should take place on the basis of the approved LPD. If subjects have been administered BESPONSA® off label, they should be excluded from the safety analysis set and analyzed separately.

Refer to the most updated LPD for the detailed information on prescription.

7.3. Study Procedures

7.3.1. Information of institution

The following will be recorded in the CRF for each patient:

- CRF number (Patient number): The investigator will sequentially assign each patient a patient identification number, which will be a 4-digit number. It will be combined with code number of institution by sponsor.
- Name of institution
- Name of department
- Name of investigator
- Date of signing data privacy statement
- Confirmation of Data Privacy Statement: If all agreement for using subject's personal and medical information, signature and date are obtained by subject or legally authorized representative, then check the box of "yes". If not, check "no" which means that case is excluded from this study.
- Confirmation of proper subject enrollment: If Subjects can be enrolled with satisfying the inclusion criteria, then check the box of "yes". If not, check "no" which means that case is excluded from this study.
- Signature of investigator: Contracted investigator must sign after identifying the CRF.

